10.2.2 Access to source data

In accordance with good clinical practices and the standards of the data protection law, data obtained in the course of a biomedical research has to be treated confidentially to guarantee the patients' privacy.

The Investigator agrees that, patient to local regulations and ethical considerations, the Sponsor representatives designee and/or and any regulatory agency have direct access to all study records, CRFs, corresponding patient medical records, study drug dispensing records and study drug storage area, and any other documents considered source documentation. The Investigator also agrees to assist the representative, if required.

11 DATA MANAGEMENT

11.1 Procedures used for data review, database cleaning and issuing/resolving data queries

11.1.1 Data entry

The personnel in charge of the study in the centres will record data to paper case report form.

A data entry mask will be created/performed as well as instructions for the data entry.

A double independent data entry will be done from the case report forms by the designed technician(s) or operator(s). The double data entry will be checked by comparison of both entries. A final quality control will be done on a part of the CRFs ($\sqrt{n+1}$).

11.1.2 Data management

Data management will consist in the different following steps:

- Redaction of a data management plan and a data validation plan.
- Redaction of annotated CRF
- Programming and validation of consistency controls
- Data Clarifications Forms (DCF) emission and database correction
- Data listings emission
- MedDRA coding of AE/ADE and WhoDrug for concomitant medications and validation of the coding by an expert
- Data Management report

11.1.3 Data Review

A study data review will be organised by AdBiostat,

Will be present a minima the sponsor and the statistician and the study monitor.

The study review will aim at determining the analysis population by:

- reviewing the conditions of study's realisation,
- determining the populations for the statistical analyses,
- specifying all the protocol's deviations as major or minor,

- reviewing the statistical analysis plan.

Following the study review, the statistical analysis populations will be defined and a report will be written and validated by AbBiostat and the Sponsor. The database will thus be corrected and locked.

11.1.4 Preparation and lock of the Database

The database will be locked upon resolution of all queries. A copy of the locked database will be sent to the Sponsor. A signed database lock form will be provided.

After the database is locked, any change to the database can only be done from database correction forms approved by the Project Manager and the Sponsor. If the database needs to be corrected, lock/unlock of the database must be clearly documented by the Project Manager in the study file.

11.2 Procedures for verification, validation and securing of electronic clinical data systems, if applicable

If applicable, the CRO will check the electronic data systems of the investigators and the company in charge of data management, according to its internal procedures.

11.3 Procedures for data retention and specified retention period

The Sponsor must archive the protocol, documentation, approvals and all other essential documents related to the study, including certificates that satisfactory audit and inspection procedures have been carried out, for 15 years.

Study centres and/or DermScan will archive the investigator files and all documents used for data treatment, as detailed below:

- All documents must be archived in a secure place and treated as confidential material.
- Paper documents relating to this study are stored maximum during one year on site before to be transmitted for archiving to an approved service provider.

Data will be archived securely as digital and paper version for 15 years from the date of dispatch of the final report's acceptance.

At the end of this period of 15 years, the study archives could be destroyed.

11.4 Other aspects of clinical quality assurance, as appropriate

In order to ensure the conformity of the studies entrusted to Good Clinical Practices and regulatory requirements, AdBiostat has implemented a quality management system..

This system consists of procedures and quality controls.

12 STATISTICS

The statistical analysis plan (SAP) will provide detailed methods for the analyses outlined below.

Any changes from the planned analyses will be described and justified in the final clinical study report.

12.1 General considerations

The statistical analysis will be performed using SAS software, version 9.2 or later.

The following descriptive statistics will be provided:

- For quantitative variables: number of observed and missing values, mean, standard deviation, minimum, median, maximum
- For qualitative variables: number of observed and missing values, frequencies and percentages per class

The significance level of 0.05 (bilateral) will be applied for statistical tests.

For the variables recorded in both eyes the descriptive analyses will be given separately for the worse eye and the contralateral eye.

The **worse eye** will be defined as follows:

- For patients with both eligible eyes, the worse eye will be:
Eye with the worse Oxford score;

if same Oxford score in both eyes: eye with the worse Schirmer score;

if same Oxford and Schirmer scores in both eyes: eye with the worse TBUT score;

if same Oxford, Schirmer and TBUT scores in both eyes: right eye.

- For patients with one eligible eye, the worse eye will be the eligible eye.

In the mITT set missing values will be imputed using the last observation available on treatment method (LOCF).

12.2 Analysis sets

The following analysis sets will be considered:

- **Safety set:** All enrolled patients having received at least one dose of IP.
Safety set will be the primary population for safety analysis.
- **Intent-to-Treat (ITT) set:** All randomized patients.
- **Modified Intent-to-Treat (m-ITT) set:** All randomized patients having received at least one dose of IP, with at least one baseline and one post-randomisation efficacy assessment on treatment.
- **Per protocol (PP) set:** All m-ITT patients without any major protocol violation.
Deviations from the protocol including violations of inclusion/exclusion criteria will be defined and assessed as “minor” or “major” in cooperation with the sponsor during a data review meeting before the database lock.

12.3 Statistical analyses

12.3.1 Study population

The number of patients in each analysis set will be provided.

Premature discontinuations from the study will be presented.

All baseline characteristics will be described:

- Demographics
- Ocular and systemic medical history

- History of Dry Eye
- Symptomatology evaluation (VAS)
- Ocular symptoms
- Far Best Corrected Visual Acuity (FBCVA) in both eyes
- OSDI score
- Schirmer test
- Slit Lamp examination (TBUT, Oxford 0-15 grading scheme Scale, Van Bijsterveld staining)
- Conjunctival hyperaemia (Mac Monnies photographic scale)

12.3.2 Efficacy Analyses

Efficacy endpoints will be analysed in m-ITT (primary analysis population for the efficacy) and PP.

The primary efficacy criterion is the change in ocular symptomatology assessed on a Visual Analogue Scale (VAS) between D1 and D42.

Estimate of the change and associated 95% confidence interval will be provided, as well as p-value for the paired t-test.

The following parameters will also be analysed:

Secondary endpoints

- Evolution of global ocular staining score according to Oxford 0-15 grading scheme (fluorescein coloration) between D1 and D42
- Evolution of Van Bijsterveld score (lissamine green coloration) between D1 and D42
- Evolution of the soothing sensation assessed by the patient between D1 and D42

Other assessments at D14

- Evolution of the ocular symptomatology on a Visual Analogue Scale (VAS) between D1 and D14
- Evolution of global ocular staining score according to Oxford 0-15 grading scheme (fluorescein coloration) between D1 and D14
- Evolution of Van Bijsterveld score (lissamine green coloration) between D1 and D14
- Evolution of the soothing sensation assessed between by the patient between D1 and D14

Other assessments at D14 and D42

- Evolution of OSDI score (Ocular Surface Disease Index) between D1 and D14 and between D1 and D42
- Evolution of the following Dry Eye symptoms between D1 and D14 and between D1 and D42: burning/irritation, stinging/eye pain, itching/pruritus, eye dryness feeling, tearing, foreign body sensation, light sensitivity graded by the patient.
- Evolution of conjunctival hyperaemia at slit lamp examination between D1 and D14 and between D1 and D42
- Evolution of Schirmer test (without anaesthesia) between D1 and D14 and between D1 and D42
- Evolution of TBUT (Tear Break-Up Time) between D1 and D14 and between D1 and D42
- Global efficacy assessment by the investigator using a 4-point verbal scale at D14 and D42.

12.3.3 Safety Analyses

Safety endpoints will be analysed in the Safety Set.

Safety analysis will be based on the following criteria:

- Ocular symptoms upon instillation: : burning/irritation, stinging/eye pain, itching/pruritus, eye dryness feeling, foreign body sensation, and other symptoms will be graded by the patient.at D14 and D42
- Far best corrected visual acuity assessment at D42
- Global ocular tolerance assessed by the investigator at D42
- Global ocular tolerance assessed by the patient at D42
- Ocular and systemic adverse events (AE)

The adverse events will be coded using the MedDRA dictionary and described according to MedDRA Preferred Term (PT) and primary System Organ Class (SOC).

The number and percentage of patients with at least one adverse event will be summarized for all AEs, study product-related AEs, serious AEs, and AEs leading to study withdrawal.

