6.6.2 Early Study discontinuation

6.6.2.1 Criteria and modalities of premature end of treatment or subject exclusion from the study

The patient may voluntarily withdraw from the study at any time without penalty and for any reason without prejudice to her future medical care (Declaration of Helsinki).

The patient must be withdrawn from the study if, in the opinion of the investigator, there is any situation or condition which puts the patient at significant risk.

The investigator may decide to withdraw a patient for the following reasons:

- Adverse event(s) or Adverse Effect(s) necessitating study discontinuation ,
- Ocular dryness worsening from baseline according to the investigator's judgement and/or ocular examination

- Lack of efficacy: if the patient or the investigator does not feel that the treatment has adequately relieved his/her symptoms,
- Patient's request.
- Other reason.

In case of withdrawal from the study, the investigator will prescribe the best appropriate treatment to the patient.

In all cases, the date and the primary reason for withdrawal, must be recorded on the case report form (CRF) and patient files (source documentation).

If a patient is prematurely withdrawn from the study for any reason, the investigator must make every effort to perform the evaluations described for the Day 42 visit.

The patient discontinued for AE(s) will be followed-up after discontinuation until the event is resolved or considered medically stable by the investigator.

If a patient is lost-to-follow-up, the investigator must do his/her best to contact the patient initially by phone, then by letter, and finally by certified mail. If no response is obtained from the patient, the investigator is encouraged to contact one of the patient's relatives or her general physician. The evidence of these contacts must be recorded in the patient files.

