3 GENERAL CONSIDERATIONS FOR DATA ANALYSES

Statistical analyses will be performed by the Biostatistics unit of AIXIAL. Analyses will be conducted with SAS® software, version 9.4 (SAS Institute, North Caroline, USA).

All tables will present the result for the overall population.

Quantitative variables (Continious data) will be summarized in summary tables indicating the number of non-missing observations (n), mean, SD, median, lower quartile (Q1), upper quartile (Q3), minimum and maximum, and 95% Confidence Interval (CI) of the mean/median.

Qualitative variables (Categorical data) will be summarized in summary tables indicating the number of non-missing observations (n), count and percentage of each modality, and 95% CI.

95% CI of a proportion will be calculated using the score method of Wilson without continuity correction:

$$\text{Lower Limit} = \frac{2np + z^2 - z\sqrt{z^2 + 4npq}}{2(n + z^2)} \quad \text{Upper Limit} = \frac{2np + z^2 + z\sqrt{z^2 + 4npq}}{2(n + z^2)}$$

With n = number of non-missing observations

p = percentage

q = 1 – p

z = 1.96 for two-sided 95%CI

Except minimum and maximum, descriptive statistics will be presented with one more decimal than the recorded value.

For all variables, the number of missing values will also be reported in the tables, but they will not be counted for the percentage calculation (categorical data).

Variables recorded for each eye will be described separately for the worse eye and for the other eye (if applicable).

An eye is eligible if it respects the inclusion criteria without exclusion criteria (ophtalmological criteria) at screening visit and inclusion visit.

The worse eye is defined as:

- For patients with both eligible eyes:
 - Eye with the worse Oxford score (higher value);
 - if same Oxford score in both eyes: eye with the worse Schirmer score (lower value);
 - if same Oxford and Schirmer scores in both eyes: eye with the worse TBUT score (lower value);
 - if same Oxford, Schirmer and TBUT scores in both eyes: right eye.
- For patients with one eligible eye: eligible eye.
- For patients with both not eligible eyes:
 - Eye with the worse Oxford score in the range ≥ 4 and ≤ 9 ;
 - if same Oxford score in both eyes: eye with the worse Schirmer score in the range ≥ 3 and ≤ 9 mm/5min;
 - if same Oxford and Schirmer scores in both eyes: eye with the worse TBUT ≤ 30 seconds;
 - if same Oxford, Schirmer and TBUT scores in both eyes: or no eye in the range for these 3 criteria right eye.

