4.2 Premature discontinuation and missing data

If a patient is prematurely withdrawn from the study for any reason, the investigator must make every effort to perform the evaluations described for the D42 visit.

In the mITT set, missing values will be imputed using the last observation available on treatment method (LOCF).

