7 SAFETY ANALYSIS

Safety endpoints will be analysed on the Safety set.

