7.4 Ocular tolerance assessment by the patient

Ocular tolerance by the patient assessed on a 4-point ordinal scale will be presented by frequency distribution for each modality and frequency distribution after regrouping 'very satisfactory' with 'satisfactory', and 'not very satisfactory' with 'unsatisfactory'.

Ocular efficacy assessment will be described at each assessment time (D14 and D42).

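### The D42 ocular tolerance percentages count only patients with a usable D42 rating, so the satisfactory rate can be too high if patients stop early for poor tolerance

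*Protocol*

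**What the plan says.** Protocol 12.3.3 lists the investigator's global tolerance rating at D42 and "Global ocular tolerance assessed by the patient at D42" among five safety criteria. SAP 7 states: "Safety endpoints will be analysed on the Safety set". SAP 7.4 says: "Ocular tolerance by the patient assessed on a 4-point ordinal scale will be presented by frequency distribution for each modality", followed by a two-group version that pools the two favourable grades; SAP 7.3 does the same for the investigator's rating. The results go to Tables 5.9 and 5.10.

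Three rules decide who is in the percentage:

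- **Denominator.** SAP 3 reports the number of missing values, "but they will not be counted for the percentage calculation (categorical data").
- **Imputation.** SAP 4.2: "In the mITT set, missing values will be imputed using the last observation available on treatment method (LOCF"). Protocol 12.1 has the same restriction to the mITT set. SAP 7 has no missing-data rule.
- **Visit allocation.** SAP 4.1 assigns days 1 to 27 to D14 and days 28 to 55 to D42. Where two records fall in one window, it keeps the one nearer the scheduled visit. It excludes a last visit made more than 24 h after the last drop.

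Protocol 6.6.2 gives "Adverse event(s) or Adverse Effect(s) necessitating study discontinuation" as a reason for withdrawal and asks the investigator to try to perform the D42 evaluations at that point.

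**The concern.** Whether a patient has a D42 tolerance rating can depend on how well the patient tolerated the product. Someone who stops because the drops hurt is more likely than others to have no usable D42 rating, and then drops out of the denominator instead of counting as not satisfied. The percentage and its Wilson interval would then describe those who tolerated the product long enough to be rated, under a table title that says Safety set.

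Safety is the trial's only secondary objective, and with a single arm there is no control rate to reveal the distortion.

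The investigator's efficacy and tolerance ratings use the same four grades at the same visits (Protocol 8.1.2.9 and 9.1.3). Under SAP 6.3 an early stopper's last efficacy rating enters the mITT summary at D42, while the last tolerance rating does not enter Table 5.9 at D42. SAP 8 does not comment on this difference.

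**Working it through.** **Step 1: who has a D42 rating.** Applying SAP 4.1 to a patient who stops early:

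| Situation | Result for D42 tolerance |
|---|---|
| Withdrawal visit on days 28 to 55, within 24 h of the last drop | Counted at D42 |
| Withdrawal visit before day 28 | Falls in the D14 window; displaced there if a D14 record lies closer to schedule; no D42 rating |
| Last visit more than 24 h after the last drop | Discarded; no D42 rating |
| No withdrawal visit attended | No D42 rating |

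Only the first row stays in the D42 denominator.

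**Step 2: formula.** Let N be the Safety set, n the patients with a usable D42 rating, m = N − n, and x the number rated satisfactory or better among the n. The planned table shows p = x/n. If a fraction r of the m unrated patients would have been satisfied, the rate over all N is (x + r·m)/N, and the excess is

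p − (x + r·m)/N = (m/N)·(p − r).

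The excess is positive only if unrated patients are less satisfied than rated ones (r < p). With r = 0 it is (m/N)·p.

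**Step 3: inputs.** The documents give no expected tolerance rate and no rate of stopping for intolerance, so there is no plan figure to reproduce for this endpoint. Protocol 6.4 and SAP 1.5 plan 55 enrolled for 50 evaluable: 55 − 50 = 5, and 5/55 = 9.1%, which the plan rounds to about 10%. That allowance covers all causes.

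Assumptions: all 55 are dosed (N = 55), three rated patients are not satisfied (so p is near 94%), and every unrated patient stopped for intolerance (r = 0).

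**Step 4: results**, with 95% intervals from the Wilson formula in SAP 3:

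| m | Planned table, x/n | Whole Safety set, x/55 | Excess |
|---|---|---|---|
| 0 | – | – | 0 |
| 1 | 51/54 = 94.4% (84.9–98.1) | 51/55 = 92.7% (82.7–97.1) | 1.7 points |
| 2 | 50/53 = 94.3% (84.6–98.1) | 50/55 = 90.9% (80.4–96.1) | 3.4 points |
| 5 | 47/50 = 94.0% (83.8–97.9) | 47/55 = 85.5% (73.8–92.4) | 8.5 points |

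Check of the last row by the formula: (5/55) × 0.94 = 0.0855. If half of the 5 would have been satisfied, the excess falls to (5/55) × (0.94 − 0.50) = 4.0 points.

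**Step 5: sensitivity to the observed rate.** With m = 5 and r = 0, the excess is 6.4 points at an observed 70% (35/50 against 35/55) and 9.1 points at 100% (50/50 against 50/55). With m = 1 it ranges from 1.3 (38/54 against 38/55) to 1.8 points (54/54 against 54/55).

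**The case against.** The strongest reply is that early stoppers do not simply vanish. The D42 evaluations are to be attempted at withdrawal, the SAP 1.2.2 schedule labels its last column as D42 or withdrawal visit with both tolerance ratings marked there, and a stopper seen on days 28 to 55 within 24 h of the last drop is counted. D14 tolerance is also tabulated on the Safety set, so a poor rating at the D14 visit is visible. The missing count is shown, so a reader can work out x/N. Reasons for discontinuation and adverse events leading to withdrawal have their own tables. Tolerance is descriptive, in a pilot study, with no test or decision rule attached. Protocol 3.4 reports few ocular adverse events with related products.

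Most of this stands, and it limits the point. It does not remove it. SAP 4.1 takes out stoppers seen before day 28 or more than 24 h after the last drop, and attendance at a withdrawal visit is best effort. The other tables do not correct the D42 percentage or its interval. A reader who computes x/N from the missing count treats every unrated patient as not satisfied, whatever the reason.

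A reader might infer that carrying the last rating forward, as for efficacy, would cure the problem. It would not. A patient satisfied at D14 who stops for intolerance on day 20 could carry a favourable rating to D42, and one who stops before any rating has nothing to carry. The different handling of efficacy and tolerance is therefore not the defect in itself.

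**Conclusion.** The point holds as a risk. The D42 tolerance percentages are conditional on having a usable D42 rating, and SAP 3, 4.1 and 4.2 together can exclude patients who stopped for poor tolerance. In the worked examples the excess is 1.7 points with one such patient, 3.4 with two, 8.5 with five, and zero with none. These figures assume 55 dosed patients, an observed rate near 94%, and no satisfied patient among the unrated.

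A reader might infer that the reported rate will be too high, or that everyone who stops for intolerance leaves the denominator. The documents support neither. The direction depends on unrated patients being less satisfied than rated ones, and some withdrawal visits do count at D42. Nor is 8.5 points an expected bias: it assigns the whole all-cause allowance to intolerance and assumes that none of the five has a usable rating.

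This is a cheap improvement worth making, not a flaw that undermines the trial.

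**What to change.** In SAP 7.3 and 7.4, state the denominator of the D42 percentages and add to Tables 5.9 and 5.10 a D42 satisfactory rate over the whole Safety set, with its Wilson interval, built as follows:

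1. Use any tolerance rating from a withdrawal visit, whatever its window under SAP 4.1 and regardless of the 24 h rule.
2. Count a patient with no rating who stopped for an adverse event or intolerance as not satisfactory.
3. For patients unrated for other reasons, show both bounds: all not satisfactory and all satisfactory. For example, with 47 satisfied, 2 unrated who stopped for an adverse event and 3 unrated for other reasons, the bounds are 47/55 = 85.5% and (47 + 3)/55 = 90.9%.

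Keep the observed-case row beside it, and do not use LOCF for tolerance.

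The cost is some SAP wording, an extra row or two in each of two tables, and a possibly slightly less favourable figure. No new data are needed: withdrawal ratings and reasons for stopping are already to be collected.

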12.3.4 Pharmacokinetic Analyses

Not Applicable

12.4 Interim Analyses

No interim analysis is planned.

13 ADMINISTRATIVE REQUIREMENTS

13.1 Amendments to protocol

Any modification to the protocol will be treated as a substantial or non-substantial modification, according to its nature, and will be submitted for opinion/approval to the Ethics Committee and/or Competent Authority if applicable.

13.2 Protocol deviations management

All protocol deviations will be managed according to DermScan Standard Operating Procedure (SOP).

A priori, patients having at least a major deviation and patients with insufficient treatment duration or without any evaluation of main criterion will be excluded from Per Protocol analysis.

Nevertheless, all deviations will be discussed during the data review which will occur before data analysis.

All deviations observed by the CRA during monitoring visits will be reported to Laboratoires Théa in the monitoring report, within maximum 10 days after the visit.

In case of serious GCP and protocol deviations the CRA should report to the CPL of Laboratories Théa by a phone call or writing an email within 24 hours.

At the study end, all deviations will be summarized and analyzed in the data review report, sent to the Sponsor.

If major deviations from an investigator are observed during monitoring, the CRA will warn the investigator of the importance to respect the protocol. An investigator who continuously violates the protocol despite CRA warnings could be excluded from the investigation after agreement of the Sponsor.

